**Feasibility metrics** will also be drawn from data collected through the ADAPT platform including the amount of time required to produce an acceptable response to a request, amount of time between notifications being sent to a user and their login to the platform. If professionals are required to generate some content, we will also estimate the cost of producing a response by tracking professional time and multiplying time by hourly pay rate. Adherence will be tracked as the number of days between a user's first and last login to the ADAPT platform as well as the number of unique days that the user visited the ADAPT platform. Users will be instructed to use the platform at least 3 times a week and we will also look at the number of weeks that users meet this expected level of use (0-8).

**Acceptability** will be assessed through quantitative ratings of the ADAPT platform at end of treatment. Additionally, we will conduct individual interviews with a subset of participants using purposive sampling to identify those who did or not benefit balancing across the treatment and control arm. Benefit will be defined as those who received at least a 25% improvement from pre-treatment score on the DASS and a shift in category (e.g., moderate to mild). Interviewers will be blind to treatment condition as well as benefit status.

**Target Outcomes** include measures of clinical symptoms, accountability, skill use and mastery, functioning, and use of the platform. We will use identical measures to the field trial. An online administered self-report assessment will measure depressive and anxiety symptoms using the DASS, accountability using the SAQ, skills use and mastery using the Frequency of Actions and Thoughts and Coping Self-Efficacy, and functioning using the PROMIS Ability to Participate in Social Roles and Activities Scale at baseline, week 4, week 8, and week 16. A telephone interview will consist of the SCID-5 for depression status and anxiety status at baseline. Use metrics include number of logins, number of times each task is completed (learning, requesting, responding), and time spent on the platform

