## **Scientific Background:**

Depression and anxiety are the most common mental health disorders in the United States with estimated 12-month prevalence rates of 18.1% and 9.5% respectively. These disorders commonly co-occur and it is estimated that over 70 million Americans each year will meet diagnostic criteria for either depression or anxiety. The human and economic burden of depression and anxiety are monumental. Depression alone is the leading cause of disability and represents the highest disease burden worldwide. Depression and anxiety have comparable impacts on quality of life and are associated with high levels of lost work productivity and increased medical costs. Efficacious treatments exist, yet many people fail to receive them. Estimates of service utilization indicate that among those meeting criteria for a mental disorder nearly 80% receive no treatment whatsoever. Barriers to treatment include costs, time, access, and stigma associated with mental health treatment. In response to these barriers, many researchers and healthcare systems have turned to technology-based treatment options, such as Internet websites and mobile apps, as alternatives to traditional face-to-face treatments. These interventions are referred to collectively as “behavioral intervention technologies” (or BITs) to distinguish them from other information and communication technologies that support healthcare more generally such as electronic medical records, clinical decision support programs, and telemedicine. As an alternative to traditional treatments, BITs allow users to access resources from anywhere in the world, at a time of their choosing. Various BITs for depression and anxiety have been evaluated with evidence supporting their efficacy. This includes Internet websites and mobile applications that draw from established evidence-based treatments such as cognitive-behavioral therapy (CBT), or transdiagnostic approaches. Despite their efficacy, one of the primary challenges that BITs face is sustained engagement. Open access BITs have particularly low rates of adherence with several studies finding only 1% of users complete all modules. Engagement tends to be better in clinical trials of BITs, with a systematic review finding completion rates ranged from 12-100% with a median of 56%. One characteristic that differentiated those trials with higher completion rates from those with lower completion rates was the use of human supported BITs. Completion rates in human supported BITs were found to be 80%, which compares favorably to face-to-face treatment. We think human support matters because it increases personal relevance of the techniques contained within the BIT and increases accountability. In traditional face-to-face CBT, the techniques factor refers to a therapist's fidelity to evidence-based practices while also acknowledging that adaptations must be made for each individual. In BIT treatments, fidelity to evidence-based principles can be very high, as it is pre-programmed. Most BITs, however, are not adapted for an individual and their needs. As such, we suggest that increasing the personal relevance within BIT treatments may increase skills use, mastery, and ultimately functioning. Personal relevance can be increased by including human supporters to clarify the use of the BIT and provide supplemental information to improve fit and use in a person's daily life. Human support also increases relational factors. In traditional face-to-face CBT, relational factors refer to the general qualities of the interaction between patient and therapist, and the therapist's ability to be attuned to their patients. In BIT treatments, relational factors have been most often described through the model of supportive accountability. In short, personally relevant therapeutic techniques and accountability drive skills use and mastery. Increased skills use and mastery results in improved functioning and clinical outcomes. Indeed, a robust literature links CBT skills use and mastery to outcome in therapy. Less research has evaluated what factors increase skills use, but BIT treatments provide a unique opportunity to explore this in detail through their ability to systematically collect data regarding skills use. This conceptual model helps illustrate why BITs that include human support have higher rates of engagement and greater efficacy. In order for BITs to reach their potential of offering scalable accessible interventions, novel strategies are needed to leverage non-professionals to support treatment engagement. This project explores enhancing BITs through crowd-powered processes. Crowdsourcing has been used in several successful technologies (e.g., reCAPTCHA, Foldit). At its core, crowdsourcing is a method for rapidly mobilizing large numbers of people to accomplish tasks on a larger scale. For effective

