## **Statistical Design**

Primary clinical outcomes for this trial will consist of symptoms of depression and anxiety. We will compare scores on depression and anxiety (DASS) between the conditions using linear mixed-models. Linear mixed-models are robust to missing data as they do not require complete case data (i.e., at every time point); thus, even participants with missing data at some assessments were included in the analysis and results are modeled on the basis of the available data. Missing data was imputed on any scale if less than 25% of the data was missing in which case the missing value was replaced by taking the mean of the non-missing items for that participant for that particular scale.

Models were a priori adjusted for age, gender, race/ethnicity as well as baseline levels of the dependent variables. For these models, we will include diagnostic status as baseline covariates in mixed-effects repeated measures model analysis using continuous measures (symptom change on DASS) as outcome variables. Mixed-models require at least 3 assessment time points and for dichotomous variables measured with telephone assessments at fewer time points we will be evaluated using descriptives, chi-square and t-tests. We will examine mediation using the Preacher and Hayes bootstrapping procedure. This procedure produces the bias-corrected and accelerated bootstrapped confidence intervals of the product of the direct pathways between condition and the mediator (a) and the mediator and the outcome (b) to estimate the indirect effect (ab).

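### Do the BCa bootstrap intervals planned for mediation report a false indirect effect often enough to need replacing?

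*SAP*

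**What the plan says.** The SAP's Statistical Design section covers mediation in two sentences. The first is: "We will examine mediation using the Preacher and Hayes bootstrapping procedure". The second begins "This procedure produces the bias-corrected and accelerated bootstrapped confidence intervals", applies these intervals to the product of two pathways, and defines those pathways as running "between condition and the mediator (a) and the mediator and the outcome (b) to estimate the indirect effect (ab".

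It gives no confidence level, number of resamples or decision rule for this analysis. The .05 in the Power section belongs to the detectable effect on the primary outcomes. The SAP does not list mediators, visits or covariates for mediation. Its general adjustment sentence is "Models were a priori adjusted for age, gender, race/ethnicity as well as baseline levels of the dependent variables", and it does not say whether this reaches the mediation models.

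The protocol supplies part of the missing detail. Under Methods, the Target Outcomes paragraph lists "accountability using the SAQ, skills use and mastery using the Frequency of Actions and Thoughts and Coping Self-Efficacy". These are measured on the same schedule as the DASS, the sentence ending "Activities Scale at baseline, week 4, week 8, and week 16". The Scientific Background says that "a robust literature links CBT skills use and mastery to outcome in therapy. Less research has evaluated what factors increase skills use". The sample is 100 participants, 50 per arm.

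**The concern.** BCa intervals for a product of coefficients are not exact at this sample size. If the platform does not move the mediator (a = 0) but the mediator does predict symptoms (b not zero), the true indirect effect is zero and the interval should exclude zero in 5% of trials. BCa can do so more often, while percentile intervals and the joint-significance test stay closer to 5%. The Scientific Background seems to describe this very case: it treats the link from skills to outcome as established and what raises skills use as the open question.

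There is a second strand. Mediators and DASS are collected at the same visits, and the mediator-outcome path is not randomised. An indirect effect computed within one visit could therefore reflect whatever moves both self-reports at once.

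At stake is a false mechanism claim carried from a pilot into the planning of a larger trial.

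**Working it through.** **The plan's own figure.** The documents state no error rate for mediation. The only calculable design figure is d = .50 with 50 per arm. One-sided: (1.645 + 0.842) × √(2/50) = 0.497, which reproduces it. Two-sided: (1.960 + 0.842) × 0.2 = 0.560, which does not. This has no bearing on the interval method; only n = 100 is carried forward.

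**Model.** X is 0/1 with 50 per arm, M = aX + e₁, Y = bM + c′X + e₂, with normal errors of SD 1 and c′ = 0 unless stated. The estimate is âb̂. The BCa limits are the bootstrap quantiles at Φ[z₀ + (z₀ ± 1.96)/(1 − k(z₀ ± 1.96))]. Here z₀ is the normal quantile of the share of resamples below the estimate, and k is the jackknife acceleration. The path sizes, the error distribution and the 95% level are assumptions.

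**False-positive rate** (10,000 trials per row, 2,000 resamples, Monte Carlo SE about 0.25 points):

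| a | b | Percentile | BCa |
|---|---|---|---|
| 0 | 0 | 0.2% | 0.5% |
| 0 | .14 | 0.9% | 2.5% |
| 0 | .30 | 3.6% | 6.6% |
| 0 | .39 | 4.6% | 7.5% |
| 0 | .59 | 5.2% | 6.6% |
| 0 | 1.0 | 5.2% | 5.7% |
| .2 | 0 | 0.8% | 2.0% |
| .5 | 0 | 3.2% | 6.2% |
| .8 | 0 | 5.7% | 8.0% |
| 1.2 | 0 | 6.1% | 7.3% |
| 2.0 | 0 | 5.7% | 6.3% |

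Smaller runs fill the gap at a = 0. BCa gave 4.8% at b = .20 and at b = .23 (percentile 2.2%), and 5.4% at b = .22 (percentile 2.6%). In that range BCa is the better calibrated of the two. With c′ = 0.5 and a = 0, BCa gave 7.6% (b = .39) and 6.6% (b = .59). With n = 80 the corresponding figures at c′ = 0 were 7.4% and 7.2%.

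So the 6-8% figure holds for a moderate or large non-null path. It does not hold for every mediator that the platform fails to move: along a = 0 the rate runs from 0.5% to 7.5%, depending on b.

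**Cost of switching** (5,000 trials per row, 1,000 resamples):

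| a | b | Power, percentile | Power, BCa | Loss (points) |
|---|---|---|---|---|
| .39 | .39 | 46.7% | 54.3% | 7.6 |
| .5 | .26 | 48.8% | 60.2% | 11.4 |
| .5 | .39 | 68.5% | 75.0% | 6.5 |
| .8 | .59 | 97.8% | 98.3% | 0.5 |

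**Comparison at matched error** (4,000 trials, 2,000 resamples). A 96.5% BCa interval had a worst-case error of 5.8%, against 5.9% for the 95% percentile interval. For the first three rows above, power was 49.1%, 51.1% and 67.3% for BCa, against 47.6%, 47.3% and 66.2% for percentile. BCa leads by 1.5, 3.8 and 1.1 points. Most of its raw power advantage is therefore bought with its higher error, but percentile is not the stronger method once the error is equalised.

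**Does the protocol place the trial in the affected region?** The Scientific Background asserts that a link exists between skills and outcome in therapy. It gives no size, does not speak of this platform, and covers skills use and mastery only. A b that is not zero need not be moderate or large.

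**Same-visit mediation.** The SAP does not commit to it, and the schedule equally allows a week-4 mediator with week-8 DASS. With a = 0.5 and no true b path, the simulated false-claim rate (joint-significance test) was 3.5% with no shared variance between mediator and outcome. It was 25-27% with 20% trait and 5% occasion variance, and 71-94% with 20-40% trait and 15-20% occasion variance. The documents give no value for these shares. The lagged alternative still gave 17-70% across the last set, so it does not cure the problem.

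**The case for a change.** The strongest case for a change is that engagement of the mechanism is a stated aim, that the SAP names the more liberal interval without giving a reason, and that percentile was lower than BCa in every false-positive row. The remedy costs one software option and a few lines of text. The mediation model is also open: three instruments, three post-baseline visits and two symptom domains make 3 × 3 × 2 = 18 same-visit combinations, with nothing choosing among them.

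Parts of this stand. The inflation is real and reproducible where one path is null and the other is moderate or large. The SAP is thin on mediation, and a single indirect effect picked from many would deserve little weight.

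It does not carry through to a change. Percentile is not clean either, reaching 6.1%, and it is markedly conservative where the non-null path is small. The change is cheap to write but costs power in a small sample. The missing detail is of the kind analysts must settle to run the procedure at all, and the protocol already names the candidate measures and their visits. The timing remedy fails on its own figures. Target engagement itself is path a, a randomised comparison that neither strand touches.

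**Conclusion.** No change follows. In the affected region BCa runs about 1-3 points above a nominal 5%; elsewhere it is near or below 5%. A full switch to percentile would give up about 7-11 points of power at moderate effects, and at matched worst-case error it offers no advantage. Reasonable statisticians would differ on the choice, and in a pilot the planned method is defensible. The indirect effect is no progression criterion, and the Power section already says the trial is not fully powered on every outcome. Readers should treat the indirect effect as exploratory, since the mediator-outcome path stays open to confounding under any interval. Analysts who wish to can show a percentile interval beside the BCa one without amending the plan.

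This rests on an assumed 95% level, normal errors, and a single-mediator linear model without the SAP's covariates or repeated measures. It also rests on path sizes that the documents do not give.

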## **Power**

We note that RFA-MH-18-706 supports pilot effectiveness research to evaluate the feasibility, tolerability, acceptability, safety and preliminary indications of effectiveness of interventions; to examine whether the intervention engages the target/mechanism that is presumed to underlie the intervention effects; and to obtain preliminary data needed as a pre-requisite to a larger-scale effectiveness trial designed to definitely test the effectiveness of interventions. As such, we are not fully powered on all outcomes. Based on our proposed sample size of 50 participants in the treatment and control conditions, we calculated the effect sizes that we would be able to detect on the primary outcomes using  $\alpha = .05$  and  $\beta = .80$  between treatment (the ADAPT platform) versus control. At this sample size, alpha-level, and power, we would be able to detect an effect size of  $d = .50$  between conditions.

These enrollment targets reflect the minimum targets that we expect and intend to enroll. Given our integration of Mental Health America's Screening-to-Supports (S2S) platform it remains possible that we can recruit a larger number who we might receive partial data on.

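### The detectable effect of d = .50 follows from the SAP's stated inputs only under an undeclared one-sided test; two-sided and unadjusted it is 0.57, and for the planned mixed model it cannot be verified

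*SAP*

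**What the plan says.** The SAP's Power section contains the only sample-size reasoning in either document. It starts "Based on our proposed sample size of 50 participants in the treatment and control conditions", sets alpha = .05 and beta = .80 for the primary outcomes, and concludes "At this sample size, alpha-level, and power, we would be able to detect an effect size of" d = .50 between conditions. The concluding sentence refers to power, so beta = .80 must mean power = .80.

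The same section qualifies the claim in two ways. It describes a pilot that is to supply preliminary data for a larger effectiveness trial and says "As such, we are not fully powered on all outcomes". It also says "These enrollment targets reflect the minimum targets that we expect and intend to enroll", and allows that more people may be recruited who give only partial data.

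The analysis itself is in the SAP's Statistical Design section. DASS depression and anxiety are compared by linear mixed models: "Models were a priori adjusted for age, gender, race/ethnicity as well as baseline levels of the dependent variables". Diagnostic status is added as a covariate in a "mixed-effects repeated measures model analysis using continuous measures (symptom change on DASS) as outcome variables". On missing outcomes it says that "even participants with missing data at some assessments were included in the analysis". The Protocol's Design section places assessments at baseline and weeks 4, 8 and 16. Neither document names the time point or contrast that d = .50 refers to.

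**The concern.** A detectable effect has meaning only relative to a particular test. The Power section gives the arm size, alpha and power, but not the sidedness, the model, the contrast, any correlation between assessments, or any loss of outcomes. The first check is whether the stated inputs give .50 for the simplest comparison. With the conventional two-sided alpha they do not.

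This is the plan's only planning figure, and the pilot is meant to inform a larger trial. A reader who assumes a two-sided test will credit the study with 80% power at d = .50. That reader cannot tell whether the figure rests on a one-sided test or on an uncredited gain from covariate adjustment. The distinction also matters at analysis, because a one-sided test changes how the p-value is read and must be declared beforehand.

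**Working it through.** **Inputs from the SAP's Power section:** n = 50 per arm, alpha = .05, power = .80, stated detectable d = .50. The effect is standardised, so SD = 1.

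**Step 1. Unadjusted comparison, complete data.** The normal approximation is

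d = (z for alpha + z for power) × √(2/n), with √(2/50) = 0.200.

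- One-sided: (1.645 + 0.842) × 0.200 = 0.497
- Two-sided: (1.960 + 0.842) × 0.200 = 0.560

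The exact noncentral t calculation (98 degrees of freedom) gives:

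| Alpha = .05 | Detectable d | Power at d = .50 | n per arm for d = .50 |
|---|---|---|---|
| One-sided | 0.501 | 79.9% | 50.15 |
| Two-sided | 0.566 | 69.7% | 63.77, so 64 |

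The SAP's .50 is reproduced by the one-sided row. Rounding does not close the gap to the two-sided row. Reading beta = .80 literally, as power of .20, does not help either: it gives d = 0.23 two-sided.

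**Step 2. Can the planned model support .50 two-sided?** Adjusting for baseline multiplies the detectable d by √(1 − r²), where r is the baseline-to-outcome correlation. Analysing change adjusted for baseline gives the same treatment contrast. The small cost in degrees of freedom from the covariates is ignored. The documents give no r, so the values below are assumptions, for a week-8 contrast:

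| r (assumed) | √(1 − r²) | 50 per arm: 0.566 × factor | 40 per arm: 0.634 × factor |
|---|---|---|---|
| 0.3 | 0.954 | 0.54 | 0.61 |
| 0.5 | 0.866 | 0.49 | 0.55 |
| 0.6 | 0.800 | 0.45 | 0.51 |

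The 40-per-arm column assumes that 20% of outcomes are lost and that those lost contribute nothing (50 × 0.8 = 40). Unadjusted, that case gives d = 0.63 and 59.8% power at .50. A mixed model that keeps partial data would lose less.

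The correlation needed for exactly .50 is r = √(1 − (0.50/d)²):

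- 50 per arm: √(1 − (0.50/0.5659)²) = 0.47
- 40 per arm: √(1 − (0.50/0.6343)²) = 0.62

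**Step 3. Averaging follow-ups.** For a baseline-adjusted mean of weeks 4 and 8, the variance factor is (1 + rf)/2 − rb², where rb is the baseline-to-follow-up correlation and rf the correlation between follow-ups. Both are assumed. At 50 per arm, two-sided:

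- rb = 0.2, rf = 0.8: factor 0.90 − 0.04 = 0.86; d = 0.566 × √0.86 = 0.52
- rb = 0.3, rf = 0.8: factor 0.90 − 0.09 = 0.81; d = 0.566 × √0.81 = 0.51
- rb = 0.5, rf = 0.7: factor 0.85 − 0.25 = 0.60; d = 0.566 × √0.60 = 0.44

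If all correlations are equal and lie between 0.3 and 0.7, averaging two or three follow-ups gives about 0.31 to 0.42 by the normal approximation. The planned model can therefore fall on either side of .50, depending on quantities the SAP does not state.

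**The case against.** The strongest reply is that 0.57 and 70% describe a two-sample t-test, which the SAP does not plan. The planned model uses baseline and repeated measures. A single week-8 contrast is a less efficient use of those data than an average over follow-ups, and under equal correlations of 0.3 to 0.7 the average detects well below .50. Even the week-8 case with r = 0.6 and 20% missing gives 0.51, almost the printed figure. On this view .50 may be reasonable or even conservative, and what is missing is documentation. The Power section never says its figure came from an unadjusted test; the close one-sided match only suggests it. The study is also a pilot that admits limited power, and enrolment may exceed 100.

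Much of this stands. The planned model may well support .50 two-sided, and the 20% loss is an assumption with no source in the documents. It does not rescue the statement as written. The Power section credits no adjustment, correlation or contrast, and plausible values lead to both sides of .50. The caveat about limited power concerns outcomes in general, whereas .50 is claimed specifically for the primary outcomes. Possible extra recruits are unquantified and may supply only partial data, and the figure is tied to 50 per arm.

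**Conclusion.** The concern holds. For an unadjusted, complete-data comparison with 50 per arm, d = .50 at 80% power requires a one-sided alpha of .05 that neither document declares. Two-sided, the detectable effect is 0.57, power at .50 is about 70%, and .50 would need 64 per arm. These results use only the SAP's own inputs.

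For the planned baseline-adjusted mixed model the figure is unverified, not disproved. Statements about that model rest on assumed correlations and loss rates. The beta = .80 label is a minor slip.

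The importance is low to moderate. A stated planning figure needs correcting or supporting, but sample size, design and conduct are unaffected.

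**What to change.** Keep N = 100 and restate the power sentence with two-sided alpha = .05, in one of two ways.

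- **Preferred:** match it to the planned model. Name the contrast (for example week 8), the assumed correlations and the assumed dropout, and give the resulting figure. As an illustration, week 8 with r = 0.6 and 20% missing gives d = 0.51. The Protocol's Methods section says "We will use identical measures to the field trial", so field-trial data, if available, could supply the correlation.
- **Otherwise:** *With 50 per arm, two-sided alpha = .05 and power = .80, an unadjusted complete-data comparison detects d = 0.57; this does not credit the covariate adjustment in the planned model.* This needs no new assumptions and says openly that it is not the planned analysis.

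If a one-sided test was intended, declare and justify it in the Statistical Design section before analysis. In every case replace beta = .80 with power = .80.

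The cost is one or two sentences. The preferred version requires choosing and defending a correlation and a dropout rate; the other prints a less favourable figure.
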